#### **6.5. Concomitant Therapy**

Appropriate documentation for all forms of premedications, supportive care, and concomitant medications including over-the-counter and analgesics use must be recorded in the eCRF. Concomitant medications and supportive care therapies must also be documented at time of discontinuations and at the short-term 30-day follow-up visit. The Lilly CRP/CRS should be contacted if there are any questions regarding concomitant or prior therapy. Refer to the prescribing information of the concomitant medications for additional information.

**Required:**

Participants who have not undergone bilateral orchiectomy are required to continue ADT with a GnRHa throughout the study. The choice of the GnRHa will be at the investigator's discretion.

**Permitted:**

Bone loss prevention treatment with bisphosphonates or denosumab per their respective approved labels. Switching between bisphosphonates and denosumab is permitted during study as long as it is in the absence of disease progression, and due to reasons including, but not limited to, tolerability.

**Use with Caution:**

Abemaciclib is extensively metabolized through oxidation by cytochrome P450 (CYP)3A. In clinical drug interaction studies,

- coadministration of clarithromycin, a strong CYP3A inhibitor, increased exposure to abemaciclib by 3.4-fold (Study I3Y-MC-JPBE), and
- coadministration of rifampin, a strong CYP3A inducer, decreased exposure to abemaciclib by 95% (Study I3Y-MC-JPBF).

Strong inhibitors of CYP3A (given via non-topical routes of administration) should be substituted or avoided if possible (Section 10.6, Appendix 6). This includes grapefruit or grapefruit juice. In particular, avoid oral administration of the very strong CYP3A inhibitor, ketoconazole. The information in Section 10.6, Appendix 6, is provided for guidance to investigators and does not preclude the use of these medications if clinically indicated.

If coadministration with a strong CYP3A inhibitor is unavoidable, investigators should reduce the dose of abemaciclib by 50 mg at the start of CYP3A inhibitor treatment. That is, for patients receiving 200 mg twice daily, reduce the dose to 150 mg twice daily. For patients who have already dose reduced to 150 mg or 100 mg twice daily for tolerability, reduce the dose further to 100 mg or 50 mg twice daily, respectively. Alternatively, the investigators may consider suspending abemaciclib for the duration of the CYP3A inhibitor medication. Dose suspensions  $\geq 28$  days must be discussed with Lilly CRP/CRS.

Upon discontinuation of the strong CYP3A inhibitor, abemaciclib may be resumed at the same dose level or re-escalated to the dose that was used before starting the strong inhibitor after a sufficient washout period (at least 3 half-lives of the strong inhibitor). Re-escalation of the abemaciclib dose requires review and approval from Lilly CRP/CRS. Inducers of CYP3A should be substituted or avoided if possible (Section 10.6, Appendix 6). Coadministration with a CYP3A inducer  $\geq 28$  days must be discussed with Lilly CRP/CRS.

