#### **4.3. Justification for Dose**

The maximum tolerated dose for abemaciclib monotherapy was defined in Phase 1 studies I3Y-MC-JPBA and I3Y-MC-JPBC (Japanese participants) as 200 mg every 12 hours, which demonstrated acceptable safety and tolerability in participants with solid cancers (Patnaik et al. 2016). Abemaciclib monotherapy is approved by the FDA for heavily pretreated HR+, HER2- MBC. The monotherapy indication is based on MONARCH 1 (NCT02102490) where abemaciclib 200 mg twice daily demonstrated a 19.7% (95% CI: 13.3, 27.5) ORR and median PFS of 6.0 months (Dickler et al. 2017).

**CCI** [REDACTED], in CYCLONE 1, abemaciclib monotherapy will be administered orally at 200 mg twice daily on Days 1 through 28 of a 28-day cycle.

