**Transporter Substrates**

At clinically relevant concentrations, abemaciclib inhibits the transporters P-glycoprotein, breast cancer resistance protein, organic cation transporter 2 (OCT2), multidrug and toxin extrusion protein 1 (MATE1), and MATE2-K. The observed serum creatinine increase in clinical studies with abemaciclib is likely due to inhibition of tubular secretion of creatinine via OCT2, MATE1,

and MATE2-K. In vivo interactions of abemaciclib with narrow therapeutic index substrates of these transporters, such as digoxin and dabigatran, may occur.

Prohibited:

With the exception of a GnRHa, no other anticancer therapy will be permitted while participants are on study intervention (including, but not limited to [anti-]hormonal agents, other CDK4 and/or CDK6 inhibitors, biologics, other antineoplastic and investigational agents, chemotherapy, radiopharmaceuticals, immunotherapy, anti-cancer vaccines, ketoconazole).

Palliative radiation or surgical intervention to treat symptoms resulting from metastatic disease is not allowed.

Drugs, or herbal/non-herbal products (e.g., saw palmetto or pomegranate) that have known prostate cancer activity and/or are known to affect PSA levels, are not permitted while on study intervention. Megestrol acetate as an appetite stimulant is not permitted.

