### 6.6.2. Dose Adjustments and Delays Abemaciclib

The toxicity dose adjustments and delays table below provides guidance for the management of treatment-emergent, related (i.e., with reasonable causal relationship with abemaciclib), and clinically significant AEs associated with abemaciclib. An investigator may suspend or reduce doses without meeting one of the criteria below and would not be considered a protocol deviation.

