#### Toxicity Dose Adjustments and Delays of Abemaciclib

Toxicity Type	CTCAE Grade	Dose Modification
Hematologic Toxicity	Grade 1 or Grade 2	No dose modification is required
	Grade 3	Suspend dose until toxicity resolves to $\leq$ Grade 2 Dose reduction is not required
	Recurrent Grade 3, or Grade 4	Suspend dose until toxicity resolves to $\leq$ Grade 2 Resume at next lower dose level
Hematologic Toxicity: If Patient Requires Administration of Blood Cell Growth Factors  Additional guidance for use of growth factors is in Section 6.5.1.2	Regardless of severity (Use of growth factors according to ASCO Guidelines)	Suspend dose for at least 48 hours after the last dose of blood cell growth factor and until toxicity resolves to $\leq$ Grade 2 Resume at next lower dose unless the dose was already reduced for the toxicity that led to the use of the growth factor
Non-hematologic Toxicity Excluding Diarrhea, ALT/AST Increased, and Interstitial Lung Disease/Pneumonitis (see below)  Additional guidance for renal monitoring is in Section 8.2.2.2 and for venous thromboembolic events is in Section 8.2.2.3	Grade 1 or Grade 2	No dose modification is required
	Persistent or recurrent Grade 2 that does not resolve with maximal supportive measures within 7 days to baseline or Grade 1.	Suspend dose until toxicity resolves to baseline or Grade 1 Resume at next lower dose level
	Grade 3 or Grade 4	
Diarrhea  Additional guidance for diarrhea management is in Section 6.5.1.1. See Section 10.7, Appendix 7, for CTCAE 5.0 grading	Grade 1	No dose modification is required
	Grade 2 that does not resolve within 24 hours to $\leq$ Grade 1	Suspend dose until toxicity resolves to $\leq$ Grade 1 Dose reduction is not required
	Grade 2 that persists or recurs after resuming the same dose despite maximal supportive measures.	Suspend dose until toxicity resolves to $\leq$ Grade 1 Resume at next lower dose level

Toxicity Type	CTCAE Grade	Dose Modification
	Grade 3, or Grade 4, or requires hospitalization	
ALT/AST Increased  See Section 8.2.2.1 for additional guidance for hepatic monitoring and Section 8.2.2.1.1 for special hepatic safety data collection. See Section 10.7, Appendix 7, for CTCAE 5.0 grading	Grade 1 or Grade 2	No dose modification is required
	Persistent or recurrent Grade 2, or Grade 3	Suspend dose until toxicity resolves to baseline or Grade 1  Resume at next lower dose

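### The flat 50 mg cut for an unavoidable strong CYP3A inhibitor offsets only a 1.33-fold exposure rise at the 200 mg starting dose (the MTD), and the protocol does not show that this is enough

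*Protocol*

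**What the plan says.** Protocol Section 6.5 (Use with Caution) states that "coadministration of clarithromycin, a strong CYP3A inhibitor, increased exposure to abemaciclib by 3.4-fold". Strong inhibitors are to be substituted or avoided where possible. If one is unavoidable, "investigators should reduce the dose of abemaciclib by 50 mg at the start of CYP3A inhibitor treatment", so a man on 200 mg goes to 150 mg twice daily. For men already lowered to 150 or 100 mg for tolerability, the instruction is to "reduce the dose further to 100 mg or 50 mg twice daily, respectively". The alternative is softer: "the investigators may consider suspending abemaciclib for the duration of the CYP3A inhibitor medication". Suspensions of 28 days or more must be discussed with the sponsor's physician or scientist. The paragraph gives no step for a man already on 50 mg twice daily.

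Section 4.3 places the starting dose at the tolerability limit: "The maximum tolerated dose for abemaciclib monotherapy was defined in Phase 1 studies", and the value given is 200 mg every 12 hours. Section 6.1 starts every participant at 200 mg twice daily. Section 8.5 describes the metabolites M2 and M20 as active. Neither document gives an interaction ratio for parent and metabolites combined.

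The only reason recorded for the current wording is in the summary of changes for amendment (b). It says that the Section 6.5 language on CYP3A modulators was brought into line with guidance, which it does not identify.

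**The concern.** An inhibitor multiplies exposure, but a fixed 50 mg cut removes a different fraction at each level: 25% at 200 mg, 33% at 150 mg and 50% at 100 mg. Protection is therefore weakest at the dose the protocol calls the MTD. The section quotes a 3.4-fold rise and then answers it with a cut that offsets far less, without explaining the gap.

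The issue is tolerability in men who follow the main instruction. Reduction is what investigators should do; suspension is something they may consider. Section 8.2.2.4 notes that serious and fatal interstitial lung disease/pneumonitis has been reported with abemaciclib. Men on 150 or 100 mg were lowered because they did not tolerate more, so for them the relevant ceiling is their own prior exposure, not only the 200 mg level.

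**Working it through.** **Inputs**
- Parent-drug ratio with clarithromycin: 3.4 (Section 6.5). This is an observed study result and cannot be re-derived. It is read here as exposure being 3.4 times the uninhibited level.
- Dose steps: 200 − 50 = 150, 150 − 50 = 100, 100 − 50 = 50 mg twice daily. These match Section 6.5.
- MTD: 200 mg every 12 hours (Section 4.3).
- Assumption, not in the documents: exposure is proportional to dose.
- Assumption, shown as a range: total-active ratio (parent plus M2 and M20) of 1.5, 2.0, 2.5 or 3.0.

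**Rise that each cut offsets** = old dose / new dose
- 200/150 = 1.33
- 150/100 = 1.50
- 100/50 = 2.00

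**Net exposure relative to the man's own prior exposure** = ratio × new dose / old dose

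| Ratio | 200 to 150 mg (×0.75) | 150 to 100 mg (×0.667) | 100 to 50 mg (×0.5) |
|---|---|---|---|
| 1.33 | 1.00 | 0.89 | 0.67 |
| 1.5 | 1.13 | 1.00 | 0.75 |
| 2.0 | 1.50 | 1.33 | 1.00 |
| 2.5 | 1.88 | 1.67 | 1.25 |
| 3.0 | 2.25 | 2.00 | 1.50 |
| 3.4 (parent) | 2.55 | 2.27 | 1.70 |

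**Net exposure relative to 200 mg without an inhibitor (the MTD level)** = ratio × new dose / 200
- 200 to 150 mg: as in the first column. At 3.4 the parent exposure matches that of 3.4 × 150 = 510 mg.
- 150 to 100 mg: 0.5 × ratio, giving 0.75, 1.00, 1.25, 1.50 and 1.70 at ratios 1.5, 2.0, 2.5, 3.0 and 3.4.
- 100 to 50 mg: 0.25 × ratio, giving 0.25 × 3.4 = 0.85 at most.

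**What would make the 200 to 150 mg step neutral?** Let p be the parent's share of active exposure before the inhibitor, and m the factor by which metabolite exposure changes. The total-active ratio is 3.4p + m(1 − p). The case most favorable to the rule is m = 0, with no metabolite left. Neutrality then needs 3.4p ≤ 1.333, so p ≤ 1.333/3.4 = 0.39. If metabolite exposure did not change (m = 1), the ratio is 1 + 2.4p, and neutrality needs p ≤ 0.333/2.4 = 0.14. The documents give neither p nor m.

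**Dose that would fully offset the parent ratio** = old dose / 3.4: 58.8 mg from 200 mg, 44.1 mg from 150 mg, 29.4 mg from 100 mg. The lowest protocol level is 50 mg (Section 6.6.1), so on the parent figure alone only the 200 mg level has a protocol dose low enough.

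**The case against.** The strongest reply is that the deciding number is missing. Clinical exposure depends on parent plus active metabolites. Blocking CYP3A plausibly lowers metabolite formation, so the combined rise may be smaller than 3.4-fold. The range used above starts at 1.5, already over the 1.33 break-even. This stands: a reader might infer that men on the 200 mg rule will reach 2.55 times MTD exposure, or must exceed it, and the documents support neither. The figure is for the parent drug and one inhibitor, and a combined ratio of 1.33 or less is not excluded. The bound above only makes it demanding: even with no metabolite left, the parent could make up no more than about 39% of active exposure.

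A reader might also infer that the rule breaches the MTD at every level. It does not. The 100 to 50 mg step stays below the 200 mg level even at 3.4, and the 150 to 100 mg step does so at any ratio under 2.0. Nor does the silence in Section 6.5 show that the sponsor has no basis. The cited guidance, or data not shown here, may supply one.

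Other controls exist. Avoidance comes first. The prohibited list includes "radiopharmaceuticals, immunotherapy, anti-cancer vaccines, ketoconazole". Section 6.6.2 adds that "An investigator may suspend or reduce doses without meeting one of the criteria below and would not be considered a protocol deviation", and toxicity triggers holds and reductions. These probably keep the number exposed small, but they do not change the default instruction for a man whose inhibitor is unavoidable.

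Finally, it is tempting to say that the protocol's own diarrhea care creates the overexposure, because Section 6.5.1.1 names fluoroquinolones and Appendix 6 lists ciprofloxacin. That is weak. The antibiotic choice is open. For Grade 3 or 4 diarrhea, or diarrhea needing hospitalization, Section 6.6.2 requires a hold and then "Resume at next lower dose level", so a man on 200 mg would be at 100 mg after both cuts. The inhibitor would have to outlast the hold, and no ratio is given for ciprofloxacin.

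**Conclusion.** The concern holds as a dosing-safety point of uncertain size. Under dose proportionality, the instructed cut leaves a man who started at 200 mg above MTD exposure whenever the active-exposure ratio is over 1.33, and the protocol offers nothing to show that the ratio is that low. The excess could be nil, modest or large, depending on data the documents do not contain. At 150 and 100 mg the question is mainly whether a man who has already needed a reduction goes above the exposure he was reduced to. That happens above ratios of 1.5 and 2.0.

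Harm is inferred. The documents give no exposure-toxicity relationship and no count of men likely to need an unavoidable strong inhibitor. A reader might infer a threat to the trial's conclusion; there is none, because the primary response-rate test and its operating characteristics do not depend on this rule. The case for acting is that the correction is cheap and the default instruction is unsupported where the dose is highest.

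**What to change.** Revise the strong-inhibitor paragraph in Section 6.5:

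- For a short inhibitor course, make the existing suspension option the default. Keep the rule that suspensions of 28 days or more are discussed with the sponsor.
- Where the inhibitor must continue too long for suspension to be practical, replace the flat 50 mg cut with a dose for each starting level. Set it from the sponsor's existing interaction data on parent plus M2 and M20, so that exposure stays at or below the man's prior level. Keep 200 to 150 mg only if those data support it, and state the basis.
- State that men on 50 mg twice daily suspend. At present they are covered only indirectly, by the suspension option or by the discontinuation step in Section 6.6.1.

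As illustration only, the highest protocol level that is exposure-neutral from 200 mg would be 100 mg at a ratio of 1.5 or 2.0 (200/1.5 = 133.3, 200/2.0 = 100) and 50 mg at 2.5 to 3.4 (200/2.5 = 80, 200/3.4 = 58.8). Blanket suspension is not proposed, because it would take long-term inhibitor users off treatment in a population with few options.

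The cost is protocol wording and use of interaction data. No new patients, procedures or analyses are needed. The downside is short interruptions or lower dosing in the men affected, who are probably few. If the sponsor's data already justify 150 mg, saying so in Section 6.5 settles that step.

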**Transporter Substrates**

At clinically relevant concentrations, abemaciclib inhibits the transporters P-glycoprotein, breast cancer resistance protein, organic cation transporter 2 (OCT2), multidrug and toxin extrusion protein 1 (MATE1), and MATE2-K. The observed serum creatinine increase in clinical studies with abemaciclib is likely due to inhibition of tubular secretion of creatinine via OCT2, MATE1,

and MATE2-K. In vivo interactions of abemaciclib with narrow therapeutic index substrates of these transporters, such as digoxin and dabigatran, may occur.

Prohibited:

With the exception of a GnRHa, no other anticancer therapy will be permitted while participants are on study intervention (including, but not limited to [anti-]hormonal agents, other CDK4 and/or CDK6 inhibitors, biologics, other antineoplastic and investigational agents, chemotherapy, radiopharmaceuticals, immunotherapy, anti-cancer vaccines, ketoconazole).

Palliative radiation or surgical intervention to treat symptoms resulting from metastatic disease is not allowed.

Drugs, or herbal/non-herbal products (e.g., saw palmetto or pomegranate) that have known prostate cancer activity and/or are known to affect PSA levels, are not permitted while on study intervention. Megestrol acetate as an appetite stimulant is not permitted.

## **6.5.1. Supportive Care**

Participants should receive full supportive care to maximize quality of life. Participants will receive supportive care as judged by the treating physician. If it is unclear whether a therapy should be regarded as supportive care, the investigator should consult with the Lilly CRP/CRS. Use of any supportive care should be recorded on the eCRF.

### **6.5.1.1. Supportive Management for Diarrhea**

When abemaciclib is initiated, the participant should receive instructions on the management of diarrhea. In the event of diarrhea, supportive measures should be initiated as early as possible. These include:

- At the first sign of loose stools, the participant should initiate anti-diarrheal therapy (e.g., loperamide) and notify the investigator/site for further instructions and appropriate follow-up.
- Participants should also be encouraged to drink fluids (e.g., 8 to 10 glasses of clear liquids per day).
- Site personnel should assess response within 24 hours.
- If diarrhea does not resolve with antidiarrheal therapy within 24 hours to either baseline or Grade 1, abemaciclib should be suspended until diarrhea is resolved to baseline or Grade 1.
- When abemaciclib recommences dosing should be adjusted as outlined in Section [6.6](#).

If diarrhea is severe (requiring IV rehydration) and/or associated with fever or severe neutropenia, broad-spectrum antibiotics, such as fluoroquinolones must be prescribed.

Participants with severe diarrhea or any grade of diarrhea associated with severe nausea or vomiting should be carefully monitored and given IV fluid (IV hydration) and electrolyte replacement.

Refer to Section [6.6](#) for guidance on dose adjustments of abemaciclib for patients with diarrhea and see Section [10.7](#), Appendix 7, for diarrhea CTCAE grades.

### 6.5.1.2. Growth Factors

Growth factors should not be administered to a participant to satisfy study inclusion criteria.

While on study treatment, growth factors may be administered in accordance with American Society of Clinical Oncology guidelines (Smith et al. 2015). Dosing of abemaciclib must be suspended if the administration of growth factors is required and must not be recommenced within 48 hours of the last dose of growth factors having been administered. Following the administration of growth factors, the dose of abemaciclib must be reduced by 1 dose level on recommencement, if a dose reduction for the specific event necessitating the use of the growth factors has not already occurred.

## 6.6. Dose Modification

Dose adjustments (suspensions and reductions) will be made based on the clinical assessment of hematologic and nonhematologic toxicities (defined as an AE possibly related to abemaciclib per investigator judgment). The CTCAE v5.0 will be used to assess AEs. Abemaciclib may be suspended for a maximum of 28 days to allow a participant sufficient time for recovery from abemaciclib-related toxicity. If a patient does not recover from the toxicity within 28 days from the time of last treatment, the patient should be considered for permanent discontinuation from abemaciclib. In exceptional circumstances, a delay >28 days is permitted upon agreement between the investigator and the Lilly CRP/CRS.

Participants undergoing non-tumor related surgical procedures should follow the guidelines below:

- For minor surgeries and procedures (for example, ambulatory), investigators should treat as clinically indicated and closely monitor any signs of infection or healing complications.
- For major surgeries, the recommendation is to suspend dosing of abemaciclib for at least 7 days before surgery and may be resumed as clinically indicated.
- Consider monitoring neutrophils and platelets before surgery and before resuming abemaciclib. The scars should be aseptic and healing process be reasonable before resuming abemaciclib.

Dose reductions for abemaciclib should be performed as shown in the table below. Abemaciclib must be reduced sequentially by 1 dose level, unless an exception is granted in consultation with the Lilly CRP/CRS. For participants requiring a dose reduction of study intervention, any re-escalation to a prior dose level is permitted only after consultation with and approval by the Lilly CRP/CRS.

### 6.6.1. Dose Reductions for Abemaciclib

Study Drug	Starting dose	Dose Reduction			
		First	Second	Third	Fourth
Abemaciclib	200 mg twice daily	150 mg twice daily	100 mg twice daily	50 mg twice daily	Discontinue

### 6.6.2. Dose Adjustments and Delays Abemaciclib

The toxicity dose adjustments and delays table below provides guidance for the management of treatment-emergent, related (i.e., with reasonable causal relationship with abemaciclib), and clinically significant AEs associated with abemaciclib. An investigator may suspend or reduce doses without meeting one of the criteria below and would not be considered a protocol deviation.

#### Toxicity Dose Adjustments and Delays of Abemaciclib

Toxicity Type	CTCAE Grade	Dose Modification
Hematologic Toxicity	Grade 1 or Grade 2	No dose modification is required
	Grade 3	Suspend dose until toxicity resolves to $\leq$ Grade 2 Dose reduction is not required
	Recurrent Grade 3, or Grade 4	Suspend dose until toxicity resolves to $\leq$ Grade 2 Resume at next lower dose level
Hematologic Toxicity: If Patient Requires Administration of Blood Cell Growth Factors  Additional guidance for use of growth factors is in Section 6.5.1.2	Regardless of severity (Use of growth factors according to ASCO Guidelines)	Suspend dose for at least 48 hours after the last dose of blood cell growth factor and until toxicity resolves to $\leq$ Grade 2 Resume at next lower dose unless the dose was already reduced for the toxicity that led to the use of the growth factor
Non-hematologic Toxicity Excluding Diarrhea, ALT/AST Increased, and Interstitial Lung Disease/Pneumonitis (see below)  Additional guidance for renal monitoring is in Section 8.2.2.2 and for venous thromboembolic events is in Section 8.2.2.3	Grade 1 or Grade 2	No dose modification is required
	Persistent or recurrent Grade 2 that does not resolve with maximal supportive measures within 7 days to baseline or Grade 1.	Suspend dose until toxicity resolves to baseline or Grade 1 Resume at next lower dose level
	Grade 3 or Grade 4	
Diarrhea  Additional guidance for diarrhea management is in Section 6.5.1.1. See Section 10.7, Appendix 7, for CTCAE 5.0 grading	Grade 1	No dose modification is required
	Grade 2 that does not resolve within 24 hours to $\leq$ Grade 1	Suspend dose until toxicity resolves to $\leq$ Grade 1 Dose reduction is not required
	Grade 2 that persists or recurs after resuming the same dose despite maximal supportive measures.	Suspend dose until toxicity resolves to $\leq$ Grade 1 Resume at next lower dose level

Toxicity Type	CTCAE Grade	Dose Modification
	Grade 3, or Grade 4, or requires hospitalization	
ALT/AST Increased  See Section 8.2.2.1 for additional guidance for hepatic monitoring and Section 8.2.2.1.1 for special hepatic safety data collection. See Section 10.7, Appendix 7, for CTCAE 5.0 grading	Grade 1 or Grade 2	No dose modification is required
	Persistent or recurrent Grade 2, or Grade 3	Suspend dose until toxicity resolves to baseline or Grade 1  Resume at next lower dose
	≥Grade 2 with total bilirubin >2× ULN, in the absence of cholestasis, or Grade 4	Discontinue abemaciclib
Interstitial Lung Disease/Pneumonitis  Additional guidance for ILD/pneumonitis monitoring is in Section 8.2.2.4. See Section 10.7, Appendix 7, for CTCAE 5.0 grading	Grade 1 or Grade 2	No dose modification is required
	Grade 2 that persists or recurs despite maximal supportive measures and does not return to baseline or Grade 1 within 7 days.	Suspend dose until toxicity resolves to baseline or Grade ≤1  Resume at next lower dose level
	Grade 3 or Grade 4	Discontinue abemaciclib

Abbreviations: ALT = alanine aminotransferase; ASCO = American Society of Clinical Oncology; AST = aspartate aminotransferase; CTCAE = Common Terminology Criteria for Adverse Events (NCI 2017); ILD = interstitial lung disease; ULN = upper limit of normal.

Note: Determination of persistent events will be at the discretion of the investigator. Recurrent toxicity refers to the same event occurring within the next 8 weeks (as measured from the stop date of the first event. As a general guidance, based on the risk/benefit balance assessment per the investigator, for a participant who experiences a new episode of Grade 3 hematological toxicity after more than 8 weeks following the last episode of the same Grade 3 hematological toxicity, the investigator may consider resuming the participant on the same drug dose should the participant satisfy the following conditions:

- The participant showed stable hematological counts (Grade ≤2) during that timeframe
- In the absence of any infectious sign or risk factor
- The participant is benefiting from study intervention.

